## 7. ANALYSIS POPULATION

### 7.1. Analysis Sets

The analysis will be performed on the complete set of patients enrolled in the study. Subgroup analyses will be carried out on the subgroups defined in Section 4.3.

### 7.2. Description of Subgroups to be Analyzed

Subgroup analysis may be performed using any relevant baseline covariates listed as below:

- Age, sex, race, ethnicity, vital signs, body weight, height, and body mass index
- T2DM history: time from date of first diagnosis to first alogliptin use, number of different previous diabetic treatments, percentage of patients with each previous diabetic treatment (eg, metformin, sulfonylurea, thiazolidinediones)
- Medical history: medications, co-morbidities, hospitalizations
- Laboratory evaluations, including HbA1c, fasting blood glucose
- Geographical region/country

## 8. STATISTICAL METHODS

### 8.1. General Statistical Considerations

This study is observational and longitudinal statistical methods will be employed for data analyses.

Statistical analysis will be performed using SAS® software (SAS Institute, Inc., Cary, North Carolina) Version 9.2 or later. Continuous variables will be summarized using the mean, the standard deviation, median, 25th percentile, 75th percentile, minimum value, and maximum value. Categorical variables will be summarized using frequency counts and percentages. Data will be listed in data listings.

No formal significance testing will be performed.

## **8.2. Data Handling Conventions**

### **8.2.1. Premature Withdrawal and Missing Data**

When a patient withdraws from the study, the reason(s) for withdrawal shall be recorded by the investigator on the relevant page of the electronic case report form (eCRF). Patients lost to follow-up will be contacted by the site in an attempt to determine the reason for study withdrawal. A maximum of 3 telephone call attempts should be documented on different days. Patients who withdraw from the study will not be replaced.

No imputation will be used for Missing data.

### **8.2.2. Definition of Baseline and Change from Baseline**

In this study, patients will attend a baseline visit followed by visits approximately at Month 3 and 6. Data collected at the baseline visit will be regarded as baseline. For HbA1c assessment, the latest HbA1c value available before the starts of alogliptin or alogliptin FDC (but within 3 months before the first dosage) will be considered the baseline value.

The change from baseline will be calculated by subtracting the baseline values from the individual post-baseline values. If either the baseline or post-baseline value is missing, the change from baseline is set to missing as well.

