4.1 Selection of Study Population

4.1.1 Inclusion Criteria

Each patient must meet all of the following criteria to be enrolled in this study:

1. Is capable of understanding the written informed consent, provides signed and written informed consent, and agrees to comply with protocol requirements. In case the patient is blind or unable to read, informed consent will also be witnessed.
2. Is 18 years of age or older.
3. Has a diagnosis of T2DM.
4. Has made the decision, along with his/her treating physician, to begin treatment with alogliptin or alogliptin FDCs.
5. Has an HbA1c value recorded at most 3 months before initiation of treatment with alogliptin or alogliptin FDCs.
6. Alogliptin or alogliptin FDCs is prescribed according to the approved label for China and Hong Kong.

Alogliptin or alogliptin FDCs will be prescribed independent of the inclusion of the patient in the study and as per standard clinical practice.

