4.1.2 Exclusion Criteria

Patients meeting any of the following criteria will be excluded from the study:

1. Has gestational diabetes or type 1 diabetes mellitus.
2. Patients who has used Dipeptidyl peptidase-4 inhibitors (DPP-IV inhibitors) or Glucagon like peptide-1 agonists (aGLP-1) within the 3 months prior to the start of alogliptin or alogliptin FDCs treatment.
3. The patients is an immediate family member, study site employee, or is in a dependent relationship with a study site employee who is involved in conduct of this study (eg, spouse, parent, child, sibling).

4. Is currently participating in a clinical trial. Participation in non-interventional registries is permitted.
5. Is being treated with any investigational drug.
6. In the opinion of the physician, the patient has any reasons of medical and non-medical in character, which should prevent patient participation in the study.

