6.1.3 Prior and Concomitant Medications

All prior and concomitant medications, including but not limited to T2DM treatments, will be collected and recorded in the eCRF as shown in the Data Collection Schedule (Table 12-1). Changes in all medication will also be collected.

For each prior and concomitant medication, the following information will be collected: medication name, start date, dose, and end date.

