6.1.4 Clinical Response to Treatment With Alogliptin or Alogliptin Fixed-Dose Combinations

6.1.4.1 HbA1c

The latest HbA1c value available before the starts of alogliptin or alogliptin FDC (but within 3 months before the first dosage) will be considered the baseline value.

The HbA1c level goal for the patient will be collected at baseline, when determined as part of standard clinical practice.

Clinical response to treatment with alogliptin or alogliptin FDCs will be evaluated based on HbA1c levels, as per the following endpoints:

- Change from baseline in HbA1c levels.
- Change in HbA1c levels over time
- Clinical response rates: incidence rates of responders. The following definitions of response will be used:
 - HbA1c level reduction to the goals of <7.0%.
 - HbA1c reduction >0.3% with no tolerability findings (hypoglycemic event, or weight gain $\geq 5\%$) (Mathieu et al 2013).

The HbA1c levels will be recorded in the eCRF as shown in the Data Collection Schedule (Table 12-1). The HbA1c levels will be obtained from any assessments performed as per standard clinical practice. No study-specific measurements will be performed. If multiple HbA1c levels are available, then the assessment closest to the visit time point will be used.

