## 4. ENDPOINTS

### 4.1. Primary Endpoint

- The primary endpoint is Change from baseline in HbA1c level on alogliptin or its FDCs therapy (V3).

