## **8.4. Efficacy Analyses**

### **8.4.1. Primary Efficacy Analyses**

Change from baseline in HbA1c level on alogliptin or its FDCs therapy will be summarized as descriptive statistics.

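### The baseline HbA1c can predate the first alogliptin dose by up to 3 months, and apart from DPP-4 inhibitors and GLP-1 agonists the plan does not track changes in other glucose-lowering drugs in that gap

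*SAP*

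**What the plan says.** SAP 8.2.2 defines baseline HbA1c as "the latest HbA1c value available before the starts of alogliptin or alogliptin FDC (but within 3 months before the first dosage". Protocol 6.1.4.1 and footnote 7 of Table 12-1 carry the same rule, and inclusion criterion 5 sets the same age limit: "Has an HbA1c value recorded at most 3 months before initiation of treatment with alogliptin or alogliptin FDCs".

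One condition applies to other glucose-lowering drugs in that window. Exclusion criterion 2 removes "Patients who has used Dipeptidyl peptidase-4 inhibitors (DPP-IV inhibitors) or Glucagon like peptide-1 agonists (aGLP-1) within the 3 months prior to the start" of alogliptin. Neither document names any other class in this context, and neither asks for a new HbA1c after a change of regimen.

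SAP 4.1 states: "The primary endpoint is Change from baseline in HbA1c level on alogliptin or its FDCs therapy (V3". SAP 8.4.1 gives the whole primary analysis: "Change from baseline in HbA1c level on alogliptin or its FDCs therapy will be summarized as descriptive statistics". Under SAP 7.1 this is done in all enrolled patients. The regression in SAP 8.4.2 includes prior diabetes therapy and therapy type, but nothing about timing relative to the baseline sample. The optional subgroup covariates in SAP 7.2 contain no such variable either.

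The medication data needed to look at this are collected. Protocol 6.1.3 says: "For each prior and concomitant medication, the following information will be collected: medication name, start date, dose, and end date".

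**The concern.** The endpoint is described as change on alogliptin therapy, but the clock for that change starts at the baseline sample, not at the first dose. If another drug is started in between and HbA1c is not measured again, the fall that drug produces before the first dose is recorded as part of the response to alogliptin. A drug stopped or reduced in the gap does the reverse.

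There is no comparator and no adjustment, so nothing in the primary summary separates the two parts. The same baseline also feeds the >0.3% response definition, the MMRM and the multiple regression. This differs from drugs started together with alogliptin or added later: here the other drug acts before the first dose.

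**Working it through.** **The plan's own figure.** The sample size rests on a standard deviation of 0.65, correlation 0.35, two-sided alpha 0.05, conditional Prob(Width) 0.9 and half-width 0.05 (Protocol 7.5, SAP 6). SD of the change = 0.65 × √(2 × (1 − 0.35)) = 0.741. The exact conditional calculation gives 899 pairs with actual probability 0.904, and 899 / 0.75 = 1198.7, rounded up to 1199. All 18 rows of the table reproduce. The point below does not affect the sample size.

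**One record under the rule (illustrative values).** HbA1c 9.0 on day −85; another oral agent started on day −80; no retest; alogliptin on day 0, when the unmeasured level is 8.3; V3 value 7.7.

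- Change by SAP 8.2.2: 7.7 − 9.0 = −1.3
- Change after the first dose: 7.7 − 8.3 = −0.6
- Part that preceded alogliptin: −1.3 − (−0.6) = −0.7

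Had V3 been 8.3, with no change at all after the first dose, the rule would still give 8.3 − 9.0 = −0.7. That exceeds the 0.3 threshold, so the patient would count as a responder if there were no tolerability findings.

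**The opposite case.** Baseline 8.3; another agent stopped; unmeasured level 9.0 on day 0; V3 value 7.7. The rule gives 7.7 − 8.3 = −0.6, while the change after the first dose is 7.7 − 9.0 = −1.3. The recorded fall is too small by 0.7.

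**Shift in the mean.** For starts, shift = p × f × e, where p is the share of analysed patients with a start in the gap and no retest, e is that drug's full HbA1c effect, and f is the fraction of e realised before the first dose. Stops enter with the opposite sign. The documents give none of p, f or e; all are assumptions. With f = 1, the upper limit:

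| Effect e (points) | p = 2% | p = 5% | p = 10% | p = 15% |
|---|---|---|---|---|
| 0.3 | 0.006 | 0.015 | 0.030 | 0.045 |
| 0.5 | 0.010 | 0.025 | 0.050 | 0.075 |
| 1.0 | 0.020 | 0.050 | 0.100 | 0.150 |

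The range is 0.02 × 0.3 = 0.006 to 0.15 × 1.0 = 0.15. If only half of the effect fell before the first dose, it would be 0.003 to 0.075. Equal shares of starts and stops with equal effects would cancel.

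**The case against.** The rule takes the latest value before the first dose. Protocol 3.1 describes HbA1c testing every 3 months after a new regimen. If alogliptin is added at the retest visit, the retest becomes the baseline and the problem disappears. The error therefore needs two regimen changes within 3 months with no measurement between them, and nothing in the documents says that this is common. This limits how often the problem can arise, but does not exclude it: a drug started soon after the baseline sample would not fall due for a 3-monthly retest inside the window, and Protocol 6.1.4.1 adds no study-specific measurement.

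The study is also descriptive, with no hypothesis and no formal testing, and a look-back baseline is a natural and consistently stated choice for it. That stands, and is why the primary summary should not change. Prior and concomitant medications are summarised under SAP 8.3.4, and prior therapy enters the regression, but neither isolates changes in the gap.

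A reader might infer that the plan places no condition at all on other glucose-lowering drugs. Exclusion criterion 2 contradicts that: it covers two classes over exactly this window. A reader might also infer net overstatement, on the view that drugs are more often started than stopped after a high HbA1c. The documents give no counts of either, so the direction is open.

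**Conclusion.** The gap is real, for glucose-lowering classes other than DPP-4 inhibitors and GLP-1 agonists, and only where therapy changed after the baseline sample without a retest. In those patients, change that occurred before the first dose is counted as change on alogliptin, and nothing planned would reveal it.

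The size is unknown. For starts, 0.006–0.15 points follows from assumed shares of 2–15% and assumed effects of 0.3–1.0 points. It is an upper range because it credits the full effect to the time before the first dose and sets no stops against starts.

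It is tempting to divide these figures by the planned half-width of 0.05 and call the bias several times the study's precision, or to compute lost interval coverage at 899 pairs. The documents do not support either comparison: SAP 9.1 says that enrolment fell far short and that 0.05 cannot be reached, and it gives no actual number. A smaller sample widens the interval but does not remove the shift.

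This is an inexpensive improvement to the plan, not evidence that the primary result is wrong.

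**What to change.** Keep the full-set mean as the primary summary. Add to SAP 8.4.1, in words such as these:

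> The V3 change in HbA1c will also be summarised, as a supportive analysis, in patients with no start, stop or dose change of any other glucose-lowering drug from the baseline HbA1c date to the day before the first alogliptin or FDC dose, both days included. The number and percentage of patients with such a change, and the median time from baseline HbA1c to first dose, will be reported. Patients whose dates are too incomplete to classify will be counted and shown separately.

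The flag comes from the medication dates and doses in Protocol 6.1.3 and the date of the baseline HbA1c. The latter is not listed by name as a collected item, but inclusion criterion 5 cannot be checked without it; the sponsor should confirm that it is in the database. SAP 8.2.1 allows no imputation and the SAP has no partial-date rule, hence the separate count.

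The cost is one derived flag and one table. The restricted set has fewer patients and a wider interval, more so after early termination and the missing V2 or V3 visits noted in SAP 9.3. The difference between the two summaries should not be read as an estimate of the bias, because patients whose treatment was changed may differ in other ways. Eligibility, visits and treatment are untouched.

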## **8.3. Study Subjects**

### **8.3.1. Disposition of Subjects**

The number and percentage of subjects who were enrolled, complete study, and who prematurely withdraw from the study will be summarized. In addition, the number and percentage of subjects who withdraw from the study will be summarized by primary reason. In addition, individual reasons for discontinuation will be listed.

### **8.3.2. Demographic and Baseline Characteristics**

Descriptive statistics (e.g., number of participants, mean, standard deviation, median, 25th percentile, 75th percentile, minimum value, and maximum value) will be generated for continuous demographic variables and baseline characteristics variables (age, height, body weight and BMI). The number and percentage of subjects in each class of the categorical demographic variables and baseline characteristics variables (sex, ethnicity and race) will be tabulated. Individual subject demographic and baseline characteristics data will be listed.

### **8.3.3. Medical History**

Medical history will include general medical history (including medications, co-morbidities, and hospitalizations), as well as specific T2DM history (including date of diagnosis and previous treatments received). They will be coded by system organ class and preferred term using the Medical Dictionary for Regulatory Activities (MedDRA) and summarized. All medical history will be listed.

### **8.3.4. Prior and Concomitant Medications**

Prior and Concomitant Medications, including but not limited to T2DM treatments, will be summarized and listed.

## **8.4. Efficacy Analyses**

### **8.4.1. Primary Efficacy Analyses**

Change from baseline in HbA1c level on alogliptin or its FDCs therapy will be summarized as descriptive statistics.

### **8.4.2. Secondary Efficacy Analyses**

The secondary HbA1c or fasting blood glucose outcomes (HbA1c clinical response rates) will be summarized by treatment as descriptive statistics and incidence rates.

If multiple HbA1c levels are available, then the assessment closest to the visit time point will be used. Clinical response rates: incidence rates of responders. The following definitions of response will be used: (1) HbA1c level reduction to the goals of <7.0%. (2) HbA1c reduction >0.3% with no tolerability findings (hypoglycemic event, or weight gain  $\geq 5\%$ ).

- HbA1c level change from baseline in subgroups with different clinical characteristics. It is proposed to use multifactorial regression model to determine factors related to effect of alogliptin and its FDCs on HbA1c level dynamics. Change from baseline in HbA1c level on alogliptin or its FDCs therapy (V3) in subgroups with different clinical characteristics will be summarized using relevant descriptive statistics and analyzed using Multiple Linear Regression with following predictors: prior therapy of DM, sex, age, cardiovascular risk group, therapy type (monotherapy or combined therapy), baseline BMI, initial glycemic control.

In addition, change from baseline in HbA1c level will be assessed and evaluated using mixed model repeated measures (MMRM) methodology. The multiple visits for each patient will be incorporated as repeated measures within each patient. Visit will be treated as a categorical predictor and baseline HbA1c level will be included as a covariate. An appropriate covariance structure will be selected to provide estimates (Least Square Means) of change from Baseline and to perform statistical analysis at Visit 3. If the unstructured covariance matrix results in a lack of convergence, the heterogeneous Toeplitz covariance structure, followed by the heterogeneous autoregressive covariance structure, followed by compound symmetry will be used. The dose-response trend hypothesis test will be conducted using the appropriate contrast statement for a linear (ordinal dose) trend. In addition, Least Squares Means, the associated standard errors and 95% confidence intervals will be displayed by each individual dose group.

[figure not shown]
- Proportion (%) of patients with diabetes mellitus type 2 whose HbA1c<7.0% will be described and presented in summary tables using absolute frequencies and percentages as well as 95% confidence intervals;
- Proportion (%) of patients with diabetes mellitus type 2 who decrease in HbA1c > 0.3% with no tolerability findings (hypoglycemic event, or weight gain  $\geq 5\%$ ) over time will be described and presented in summary tables using absolute frequencies and percentages as well as 95% confidence intervals;
- Change from baseline in fasting plasma glucose level on alogliptin or its FDCs therapy over time (V1-V2-V3) will be summarized using relevant descriptive statistics and analyzed with mixed model with repeated measures using clinical characteristics as independent factors;
- Change from baseline in HbA1c level on alogliptin or its FDCs therapy over time (V1-V2-V3) will be summarized using relevant descriptive statistics and analyzed with mixed model with repeated measures using clinical characteristics as independent factors;
- Proportion (%) of patients who remain on Alogliptin or its FDCs treatment (V2-V3) and information of dose escalation or reduction (V2-V3) will be described and presented in summary tables using absolute frequencies and percentages as well as 95% confidence intervals.

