3.1.1 Rationale of Study Design

This study is intended to describe the real-world clinical response as assessed by HbA1c level change from baseline in a real world setting. An observational design is adequate to fulfill the primary objective of this study, as it will not interfere with the prevailing standard of care for patients with T2DM.

The proposed data collection schedule has been designed to have a negligible impact on the site standard clinical practice for the treatment of patients with T2DM, and thus to ensure the validity of the study results. Although the patients included in this study will be treated as per standard clinical practice and will not receive any direct benefit from the study, the study will provide an opportunity to gain a better understanding on what type of patients are being treated with alogliptin or alogliptin FDCs, and what type of patients benefit the most from treatment with alogliptin or alogliptin FDCs in a real-world setting as this is different from the clinical trial setting. This will allow providing real-life data to prescribers to best serve patients, and will contribute to increase scientific knowledge about alogliptin and alogliptin FDCs.

The primary endpoint of HbA1c level, as well as the additional secondary endpoints related to HbA1c levels reduction to the goal <7.0%, will be achieved by collection of available HbA1c levels, a well-documented biomarker of disease control in T2DM. To preserve the observational nature of the study, this information will be obtained from any assessments performed as per standard clinical practice, and no study-specific measurements will be performed.

The proposed number of patients (approximate 1199 enrolled patients) and the planned duration of the study (6 months or up to loss to follow-up or death, whichever occurs first) are considered to be sufficient to achieve a satisfactory degree of precision and to provide valuable data on the study objectives, as described in Section 7.5.

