## 3. STUDY DESIGN

This is an observational, prospective, multicenter study in adult patients with T2DM diagnosis who have made the decision, along with their treating physician, to begin treatment with alogliptin or alogliptin FDCs.

The purpose of this study is to observe alogliptin and alogliptin FDCs utilization patterns, as well as clinical response to treatment with alogliptin or alogliptin FDCs, in standard clinical practice. No investigational product will be administered in this study.

The observational study will include approximate 1142 patients with T2DM treated with alogliptin or alogliptin FDCs in approximately 40 sites.

The planned maximum duration of this study per patient will be 6 months or up to loss to follow-up or death, whichever occurs first. In this study, Patients will attend a baseline visit followed by visits approximately at Month 3 and 6. Patients will not be asked to travel to the site only for the purpose of this study; the study visits will be performed during regular doctor's appointments.

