### 4.2. Secondary Endpoint

The secondary endpoints related to real-world clinical response to alogliptin or alogliptin FDCs are the following:

- Clinical response rates: incidence rates of responders. The following definitions of response will be used as secondary endpoints:
  - Change from baseline in HbA1c level on alogliptin or its FDCs therapy in subgroups with different clinical characteristics (V3).
  - HbA1c levels reduction to the goals of <7.0% (V3).
  - HbA1c reduction >0.3% with no tolerability findings (hypoglycemic event, or weight gain  $\geq 5\%$ ) (V3).
  - To evaluate the effect of alogliptin and its FDCs on fasting blood glucose dynamics in patients with diabetes mellitus type 2 over time (V1-V2-V3).
- To evaluate the effect of alogliptin or alogliptin FDCs on glycosylated hemoglobin (HbA1c) level dynamics in patients with diabetes mellitus type 2 in dependence on clinical characteristics (V1-V2-V3).
- ADRs, SAEs, and AESIs.

The secondary endpoints related to alogliptin or alogliptin FDCs utilization patterns are the following:

- Percentage of patients who remain on treatment with alogliptin or alogliptin FDCs (V2-V3).
- Time to alogliptin or alogliptin FDCs dose escalation or dose reduction (V2-V3).

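### The single-arm regression of HbA1c change on initial glycaemic control cannot identify factors related to the effect of alogliptin, because regression to the mean alone gives a negative baseline slope

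*SAP*

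**What the plan says.** SAP 3 describes one treated cohort: "This is an observational, prospective, multicenter study in adult patients with T2DM diagnosis who have made the decision, along with their treating physician, to begin" alogliptin or a fixed-dose combination. Neither document has a comparator group.

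SAP 8.4.2 introduces a multiple linear regression with this purpose: "It is proposed to use multifactorial regression model to determine factors related to effect of alogliptin and its FDCs on HbA1c level dynamics". Its outcome is "Change from baseline in HbA1c level on alogliptin or its FDCs therapy (V3) in subgroups with different clinical characteristics". The seven predictors are prior diabetes therapy, sex, age, cardiovascular risk group, therapy type (mono or combined), and finally "baseline BMI, initial glycemic control". The last of these is not defined further. Protocol 7.8.2 gives the same model.

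Under SAP 8.2.2 the baseline is one measurement, "the latest HbA1c value available before the starts of alogliptin" or the combination, within 3 months before the first dose. Change is the later value minus this one.

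The language of effect recurs. SAP 4.2 lists as a secondary endpoint "To evaluate the effect of alogliptin or alogliptin FDCs on glycosylated hemoglobin (HbA1c) level dynamics" according to clinical characteristics. Similar wording stands in SAP 2.2, Protocol 2.2, Protocol 7.2 and the Protocol Abstract. The design rationale in Protocol 3.1.1 hopes to learn "what type of patients benefit the most from treatment with alogliptin or alogliptin FDCs in a real-world setting". Neither document mentions regression to the mean or limits how the regression coefficients may be read.

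**The concern.** Two features combine. First, the baseline measurement is subtracted to form the outcome and also enters the model as a predictor. A patient whose single baseline value happened to be high will tend to show a larger fall, and one whose value happened to be low a smaller fall or a rise, whatever the drug does. Second, with no untreated or comparator group, nothing shows how much of the baseline slope would have appeared anyway.

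A negative coefficient for initial glycaemic control is therefore expected even with no variation in drug effect. Read under the model's stated purpose, it would look like evidence that poorly controlled patients respond better. Prior therapy and mono versus combined therapy are plausibly related to baseline HbA1c, so their coefficients can carry part of the same artefact.

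**Working it through.** **Inputs.** Correlation 0.35, SD 0.65 (range 0.60 to 0.70), half-width 0.05, Prob(Width) 0.9, two-sided alpha 0.05 and dropout 25%, all from Protocol 7.5 and SAP 6. Correlations of 0.5, 0.7 and 0.9 are assumptions, used to show a range.

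**1. Reproducing the plan's figure.** SD of change = SD × √(2(1 − ρ)) = 0.65 × √1.30 = 0.741. The smallest number of pairs giving a conditional probability of at least 0.90 that the half-width is at most 0.05 is 899 (actual probability 0.904), as stated. Enrolment is 899/0.75 = 1198.7, so 1199, also as stated. The match requires 0.65 to be the SD of each measurement. Read as the SD of change, it gives 697 pairs (unconditional probability). The sample size is not in question. This step fixes what 0.65 and 0.35 mean.

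**2. Baseline slope under an identical effect.** Let V3 = V1 + a constant + noise, with equal SDs at both visits and correlation ρ. Then slope of change on baseline = Cov(V3 − V1, V1)/Var(V1) = ρ − 1. The constant drug effect cancels. The share of variance explained is (1 − ρ)/2.

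**3. Gap between halves.** The mean of a standard normal above its median is 0.798, so the gap in change between patients above and below the median baseline is (1 − ρ) × 0.65 × 2 × 0.798.

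| ρ | Slope per 1% HbA1c | R² | t at 899 pairs | Gap in change (points) |
|---|---|---|---|---|
| 0.35 (plan) | −0.65 | 0.325 | −20.8 | 0.67 |
| 0.5 (assumed) | −0.50 | 0.25 | −17.3 | 0.52 |
| 0.7 (assumed) | −0.30 | 0.15 | −12.6 | 0.31 |
| 0.9 (assumed) | −0.10 | 0.05 | −6.9 | 0.10 |

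Simulation at ρ = 0.35 (2000 runs of 899 pairs) gave a mean slope of −0.65, with p < 0.05 in every run, whether the constant effect was 0 or −0.5. For the slope to vanish at ρ = 0.35, the V3 SD would have to be 1/0.35 = 2.86 times the baseline SD.

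**4. Gap against its own precision.** At ρ = 0.35 the SD of change within each half is √(0.741² − (0.674/2)²) = 0.660. The 95% half-width of the contrast at 899 pairs is 1.96 × 0.660 × 2/√899 = 0.086, and 0.674/0.086 is about 8. At an illustrative 100 pairs the half-width is 1.96 × 0.660 × 2/√100 = 0.26, with the same expected gap.

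**5. Spill-over to other predictors.** Illustrative simulations at ρ = 0.35 used a two-level factor unrelated to drug effect, with an assumed latent correlation of 0.3. The entries are its coefficient in HbA1c points.

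| Factor is tied to | Unadjusted | Two-level baseline category | Continuous baseline |
|---|---|---|---|
| The measured baseline value | −0.20 | −0.07 | 0.00 |
| The patient's stable HbA1c level | 0.00 | +0.08 | +0.12 |

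Continuous baseline removes the artefact in the first case. In the second, conditioning on one error-prone value creates a spurious coefficient, and continuous entry does not help.

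**The case against.** The strongest reply is that the plan is descriptive. The primary objective is to describe, SAP 5 states no hypothesis, SAP 8.1 and Protocol 7.8 rule out formal significance testing, and the regression is only proposed. A reader might infer that the study will announce that poorly controlled patients benefit most. The documents do not say so. The phrase about who benefits most is in the design rationale of Protocol 3.1.1, not in the secondary-analysis text. This limits the consequence but does not remove it: the model's stated purpose is still to find factors related to the drug's effect, and a coefficient or subgroup table can be misread without a p-value.

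A second reply is that 0.35 is a planning value with no derivation shown. A low correlation can reflect measurement noise, within-patient change, changes in other therapy or real variation in effect. This stands. The −0.65 slope is what arises without effect modification, not proof that there is none, and the range of correlations is the fair statement of size.

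Third, the gap of 0.67 invites comparison with the plan's 0.05 half-width, a ratio of about 13. That is not like for like, because 0.05 applies to the overall mean change. The ratio of about 8 is the proper one.

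Fourth, the plan never says that initial glycaemic control is a category, and the companion mixed model already includes baseline HbA1c. Both are true. The mixed model, however, conditions on the same single value and does not turn its coefficient into a measure of differential effect.

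Finally, SAP 9 reports early termination with far fewer patients than planned. Fewer pairs widen the intervals but leave the expected slope and gap unchanged.

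**Conclusion.** The concern holds as a limit on interpretation. The proposed regression cannot show which patients gain more from the drug, because a negative baseline slope is expected under an identical effect in everyone and the single-arm design cannot separate the two. The size depends on the correlation: a slope from −0.65 at 0.35 to −0.10 at 0.9, and a gap between halves from 0.67 to 0.10 points. These figures assume equal SDs at V1 and V3, normality, and a per-measurement SD of 0.65. The spill-over figures are illustrative.

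The documents do not support the stronger inferences that no true differential effect exists or that the primary result is undermined. The primary descriptive summary and the sample size stand.

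**What to change.** 1. In SAP 8.4.2 and Protocol 7.8.2, state the purpose of the regression as finding factors associated with HbA1c change. Make the matching change where the effect of the drug is to be evaluated: SAP 2.2 and 4.2, Protocol 2.2 and 7.2, and the Protocol Abstract. As the study has been terminated early, the SAP or study report is the practical place to qualify the aim in Protocol 3.1.1.
2. Do not report the coefficient for initial glycaemic control, or change by baseline-HbA1c subgroup, as differential drug effect.
3. Define initial glycaemic control and enter it as continuous baseline HbA1c, consistent with the mixed model. Note that this deals with predictors that follow the measured baseline but not with those tied to stable HbA1c, so it cannot replace the rewording.
4. State that regression to the mean, added therapies and the lack of a comparator limit interpretation.

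The cost is wording, one covariate definition and a limitation paragraph, with no new data. The downside is a weaker claim about who benefits most.
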